Participants that were cleared to exercise by a cardiologist were enrolled in *Small Steps for Big Changes* (SSBC), a 4-week community-based DPP. The full details of SSBC, including its efficacy and effectiveness in laboratory and community settings have been published previously. Briefly, SSBC consists of six one-on-one sessions with a trained community coach (i.e., fitness professionals working at a recreation facility) over a 4-week period, delivered either virtually or in-person at one of three community recreation facilities. Each session entails a brief behavioral counselling component during which trained coaches use motivational interviewinginformed techniques to foster participants' self-efficacy and determination for changing and maintaining healthy nutritional and physical activity behaviors. Information pertaining to specific content delivered during sessions and fidelity of program delivery by community coaches has been previously published. Community coaches subsequently follow up with participants 1, 6, and 12 months after the 4-week supervised intervention.

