For full details regarding outcome measures of this trial, please refer to the trial registry details. Briefly, individuals' perceived autonomy support was measured post-intervention to discern any differences between conditions. Within-condition changes in motivation regulation from pre-intervention were assessed post-intervention and 6-months post-intervention. Within-condition changes in free-living physical activity and cardiorespiratory fitness were assessed from pre-intervention to 6-months post-intervention. Between-condition differences were also assessed at each timepoint for motivation regulation, physical activity, and cardiorespiratory fitness. A manipulation check was conducted with a sub-set of participants to determine the modality of exercise that participants engaged in during the 6-month follow-up period.

Changes Consequent to COVID-19

Recruitment for this trial commenced in February 2019 using a monthly rolling recruitment strategy (~6-10 participants/month). Originally, follow-up appointments were planned to discern changes in the outcome variables 12 months post-intervention. However, at the beginning of the 12-month follow-up phase (February 2020), the COVID-19 pandemic resulted in the curtailment of all research activities at the host institution. A total of 75 participants were not able to complete follow-up assessments, and data were therefore lost for this first cohort. Recruitment for this trial could not be resumed until October 2021. To complete data collection in a timely manner given these unanticipated resource constraints, follow-up assessments were conducted 6 months post-intervention for this second cohort as opposed to the original 12-month timepoint. The complete loss of data on the first 75 participants to enroll in the trial and subsequent curtailment of research for more than 1.5 years therefore significantly limited the final study sample size.

Sample Size

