Statistical analyses were performed using R (version 4.3.0) or SPSS (version 28). Anthropometric and demographic information were summarized as means (standard deviations) for continuous data and N (%) for categorical data, unless otherwise stated. Medians and ranges are reported for 6-month exercise modality frequency to represent the central tendency and dispersion more accurately.

Blinded data analysis was completed on an intention-to-treat (ITT) basis as all randomized participants were included in the analyses irrespective of their program compliance. No missing data were imputed as per contemporary guidelines. A linear model with restricted maximum likelihood estimation (REML) was used to detect a between-condition difference in perceived autonomy support post-intervention. The model included treatment condition (i.e., HIIT, MICT, or CHOICE) as a fixed factor, and stratified allocation factors (i.e., age and biological sex) as covariates. Similarly, linear mixed models were used to analyze changes in motivation regulation, physical activity behavior, and cardiorespiratory fitness between conditions. Linear mixed models included fixed effects for timepoint (pre-intervention, postintervention, 6 months post-intervention), treatment condition, as well as the interaction thereof, stratified allocation factors, and a random effect for participants to address non-independence of measurements arising due to the repeated-measures design of this study. Model assumptions were assessed visually using normal probability plots and residuals vs. fitted values plots (i.e., homoscedasticity). Bonferroni-adjusted preplanned pairwise comparisons of estimated marginal means were conducted to derive effect estimates and accompanying 95% confidence intervals (CIs) after adjusting for included covariates. A two-sided alpha of .05 was used for all statistical analyses.

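### Read as written, the three-visit motivation models assume one correlation for visits about 1, 6 and 7 months apart, which can understate the standard error of the pre-to-6-month change

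*Combined protocol and SAP*

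**What the plan says.** The Statistical Methods section describes the mixed models in one sentence. Their fixed part is "Linear mixed models included fixed effects for timepoint (pre-intervention, postintervention, 6 months post-intervention), treatment condition, as well as the interaction thereof", plus the stratification factors. Their random part is "a random effect for participants to address non-independence of measurements arising due to the repeated-measures design of this study". No residual covariance structure, random slope or degrees-of-freedom method is given. The only model checks listed are normal probability plots and plots of residuals against fitted values. Pairwise comparisons are Bonferroni-adjusted, and "A two-sided alpha of .05 was used for all statistical analyses".

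The Outcomes section sets the contrasts. For motivation: "Within-condition changes in motivation regulation from pre-intervention were assessed post-intervention and 6-months post-intervention". In addition: "Between-condition differences were also assessed at each timepoint for motivation regulation, physical activity, and cardiorespiratory fitness". The other two repeated outcomes have only two visits: "Within-condition changes in free-living physical activity and cardiorespiratory fitness were assessed from pre-intervention to 6-months post-intervention".

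The spacing comes from two places. The section on Small Steps for Big Changes describes "six one-on-one sessions with a trained community coach" over 4 weeks. The section on COVID-19 changes says that "follow-up assessments were conducted 6 months post-intervention for this second cohort as opposed to the original 12-month timepoint". The three motivation visits are therefore about 1 month (pre to post), 6 months (post to follow-up) and 7 months (pre to follow-up) apart.

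**The concern.** A single random intercept with independent residuals is a compound-symmetry model: one variance for all visits and one correlation for all pairs. Every change is then judged against the same averaged within-person variance. If the true correlations differ, that average is too small for pairs correlated less than average and too large for pairs correlated more.

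The pre-to-6-month pair is the one most likely to be correlated below average. It has the longest gap, and the whole intervention lies inside it. It also carries the long-term motivation question. An understated standard error there means confidence intervals that are too narrow and too many false positives. The two listed diagnostic plots do not display correlation between visits, so they would not reveal the problem.

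**Working it through.** **Inputs from the documents.** Three motivation visits with gaps of about 1, 6 and 7 months; one participant effect; two-sided alpha .05; Bonferroni adjustment; N = 77 in three arms (about 26 per arm). The plan gives no visit correlation, visit-specific SD or standard error for motivation, so there is no figure of its own to reproduce.

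**Assumptions.** All correlations below are assumed. They are written in the order pre-post / post-6m / pre-6m. Variances are equal and data complete, unless stated.

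**Formula.** For change between visits j and k in an arm of size n:

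- true variance = 2σ²(1 − ρ_jk)/n
- variance under compound symmetry = 2σ²(1 − ρ̄)/n, where ρ̄ is the mean of the three correlations
- q = model SE / true SE = √[(1 − ρ̄)/(1 − ρ_jk)]

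The sample size cancels. The same ratio applies to differences in change between arms. Large-sample type I error is 2Φ(−1.96q) unadjusted. With Bonferroni over three comparisons (alpha .05/3 = .0167; the family size is assumed, since the plan does not state it), it is 2Φ(−2.394q).

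**One case in full, .7/.6/.5.** ρ̄ = (.7 + .6 + .5)/3 = .6.

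- Pre-6m: q = √(.4/.5) = 0.894, so the SE is 11% too small. Type I error is 2Φ(−1.753) = .080 unadjusted and 2Φ(−2.141) = .032 against .0167.
- Pre-post: q = √(.4/.3) = 1.155, so the SE is 15% too large. Type I error is .024 unadjusted.

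**The range.**

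| Assumed correlations | q, pre-6m | Type I, pre-6m | Bonferroni rate, pre-6m (.0167) | q, pre-post | Type I, pre-post |
|---|---|---|---|---|---|
| .60/.55/.50 | 0.949 | .063 | .023 | 1.061 | .038 |
| .65/.60/.55 | 0.943 | .065 | .024 | 1.069 | .036 |
| .70/.50/.50 | 0.931 | .068 | .026 | 1.202 | .018 |
| .70/.60/.50 | 0.894 | .080 | .032 | 1.155 | .024 |
| .80/.50/.40 | 0.850 | .096 | .042 | 1.472 | .004 |
| .80/.70/.50 | 0.816 | .110 | .051 | 1.291 | .011 |
| .50/.70/.50 (intervention weakens pre-post) | 0.931 | .068 | .026 | 0.931 | .068 |
| .60/.60/.60 (equal) | 1.000 | .050 | .017 | 1.000 | .050 |

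**Simulation check.** With 20,000 runs, three arms of 26 and no true difference in change between arms, the random-intercept model under .7/.6/.5 rejected in .079 of runs for pre-6m and .0225 for pre-post. An unstructured covariance gave .053 and .049. Under .8/.7/.5 the random intercept gave .109 and .012. Under .5/.7/.5 it gave .066 and .067.

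**Arm differences at one visit.** Their variance is 2σ²/n, which contains no correlation between visits, so q = 1 with complete data. Simulation with N = 77 (800 runs per case) gave ratios of 0.96 to 1.05 with complete data, and 0.96 to 1.02 with 20% missing at 6 months. These are within simulation noise or slightly below 1.

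**Physical activity and fitness.** With two visits there is only one correlation, so requiring equal correlations restricts nothing.

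**The case against.** **The covariance is unstated, not fixed.** R and SPSS can combine a participant effect with a structured residual covariance. This stands. Compound symmetry is the natural reading of the sentence, not something the plan declares.

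**The correlations and the direction are assumed.** A reader might infer that every 6-month motivation contrast has too small a standard error and every 4-week contrast too large a one. The documents do not support that. They give no correlations. The programme lies between pre and post and could weaken that correlation, in which case the pre-to-post error is also too small. Equal correlations give no error. Arm differences at 6 months are also 6-month contrasts, and they are essentially unaffected. What survives is narrower: decay over time and disruption by the intervention both put the pre-to-6-month correlation below the average.

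**Bonferroni softens the effect.** This is partly right. For within-condition changes, with adjustment over an assumed three visit pairs, simulated familywise error was .046 under both .7/.6/.5 and .65/.60/.55, and .056 under .8/.7/.5. A reader should therefore not infer that adjusted pre-to-6-month tests generally exceed .05. But the rate for that comparison was .031, .025 and .051 respectively, each above its .0167 share. For arm differences in change, familywise error was .081 under .7/.6/.5.

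**Missing follow-up.** It is tempting to add that a wrong covariance biases the estimates. That depends on why data are missing, and the documents give neither amount nor pattern among the 77. No such bias is claimed here.

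**Limited reach.** The sample size rests on perceived autonomy support, which is measured once and is untouched.

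**Conclusion.** The point holds for the pre-to-6-month change in motivation regulation and for arm differences in that change. It assumes that the model is a random intercept with independent residuals and that the pre-to-6-month correlation is below the average of the three. Over the unequal patterns tried, the standard error is about 5 to 15% too small in most cases and 18% in the steepest (.8/.7/.5). Unadjusted type I error is about 6 to 11%. The per-comparison rate after Bonferroni over an assumed three comparisons is about .02 to .05 against .0167. The documents cannot narrow this range.

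The pre-to-post standard error may be too large or too small. The equal-correlation restriction leaves single-visit arm differences and the two-visit outcomes essentially unaffected. Variances that change from visit to visit are a separate matter, and these figures do not cover them. This is a cheap improvement, not evidence that a reported result is wrong.

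**What to change.** For the motivation models, state the covariance structure and make it unstructured across the three visits, fitted by REML with Kenward-Roger degrees of freedom. Name a fallback in advance if it does not converge: heterogeneous AR(1) or Toeplitz. In their standard forms both treat the visits as evenly spaced, so they give pre-post and post-6m the same correlation. They are second best, but they do let pre-6m differ. The activity and fitness models need at most visit-specific variances.

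The document is written in the past tense and reports on 77 participants. Where results already exist, report this analysis beside them rather than silently replacing them.

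The cost is 6 covariance parameters instead of 2, and some degrees of freedom. With complete data the error degrees of freedom for a change fall from about (77 − 3) × 2 = 148 to 77 − 3 = 74. The two-sided 5% critical value then rises from 1.976 to 1.993, or 0.8%. If the true correlations are in fact equal, the unstructured model still held its level in simulation (.049). The change is one sentence in the plan, plus a rerun where the analysis is already done.

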CHOICE Study Protocol with Statistical Analysis Plan

NCT Number: NCT03576924

Document Date: March 3, 2025

Participants

Potentially eligible participants for this trial were referred by their family physician to partake in a community-based DPP (Small Steps for Big Changes) if they had a hemoglobin A1c (HbA1c) test within the American Diabetes Association's (ADA) prediabetes range of 5.7%-6.4% in the last 6 months. Potential participants who did not have a recent HbA1c test result but scored a 5 or higher on the ADA diabetes risk assessment were also invited to participate. Advertisements for recruitment included pamphlets in healthcare offices, website adverts, social media posts, and word of mouth. Potential participants were screened by a member of the research team via phone to ascertain if they met the following inclusion criteria: between 18 and 75 years of age, engaged in two or fewer bouts of purposeful physical activity per week in the last 6 months, had a recent HbA1c test result between 5.7%-6.4% or an ADA risk assessment score >5, and were cleared to engage in physical activity as determined by the Get Active Questionnaire. Participants were excluded from this trial if they had a previous diagnosis of T2D, were taking glucose-lowering medications or beta-blockers, had a history of cardiovascular disease, were diagnosed with uncontrolled hypertension (resting blood pressure >160/90), or had explicit contraindications to exercise. All participants provided written informed consent prior to enrollment.

Predicted Maximal Exercise Testing

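### The mixed model as written gives physical activity one variance at both visits; if activity is less spread at entry than at 6 months, the 6-month between-condition standard errors are too small.

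*Combined protocol and SAP*

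**What the plan says.** All quotations are from the combined protocol and SAP.

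- **Entry (Participants).** At phone screening, participants had to have "engaged in two or fewer bouts of purposeful physical activity per week in the last 6 months".
- **Visits (Outcomes).** "Within-condition changes in free-living physical activity and cardiorespiratory fitness were assessed from pre-intervention to 6-months post-intervention". The Statistical Methods section lists three timepoints for the mixed models in general, but for physical activity only these two are described.
- **Contrasts (Outcomes).** "Between-condition differences were also assessed at each timepoint for motivation regulation, physical activity, and cardiorespiratory fitness". The 6-month comparison of conditions is therefore a planned analysis.
- **Model (Statistical Methods).** "Linear mixed models included fixed effects for timepoint (pre-intervention, postintervention, 6 months post-intervention), treatment condition, as well as the interaction thereof", plus the stratification factors and "a random effect for participants to address non-independence of measurements arising due to the repeated-measures design of this study". No visit-specific variance, unstructured covariance or robust standard error is named.
- **Tests (Statistical Methods).** "Bonferroni-adjusted preplanned pairwise comparisons of estimated marginal means were conducted to derive effect estimates", and "A two-sided alpha of .05 was used for all statistical analyses".
- **Checks (Statistical Methods).** "Model assumptions were assessed visually using normal probability plots and residuals vs. fitted values plots (i.e., homoscedasticity"). No action is stated for the case where the plots look bad.

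The documents give no SD of physical activity at either visit.

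**The concern.** A participant random effect with a single residual variance forces the same total variance on both visits. With two visits this is purely a question of variance, because there is only one correlation to model. If the true variances differ, the fitted value settles near their average. That average is too large for the less spread visit and too small for the more spread one.

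There is a reason to expect a difference here. The entry rule restricts reported activity at the start. At 6 months the restriction acts only indirectly, through the correlation of activity over time. If spread is larger at 6 months, the three pairwise comparisons of HIIT, MICT and CHOICE at that visit have confidence intervals that are too narrow and a false-positive rate above the stated level. Bonferroni does not repair this, because it divides alpha but leaves the standard error as it is. With N = 77, about 26 per condition, an understated standard error can make noise look like a difference.

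**Working it through.** **Inputs.** From the documents: two visits, three conditions in 1:1:1 allocation, N = 77, two-sided alpha 0.05. Assumed: three Bonferroni pairs, so 0.05/3 = 0.0167 each; and r = baseline SD / 6-month SD, which the documents do not give. The plan states no figure on this point that could be reproduced.

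**Step 1: standard error at 6 months, complete data.** Write s0 and s1 for the SDs at baseline and 6 months. The random-intercept model puts (s0² + s1²)/2 at each visit; the 6-month contrast needs s1². So

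model SE / true SE = sqrt(((s0² + s1²)/2) / s1²) = sqrt((1 + r²)/2),

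and the true error of a test at nominal level α is 2 × [1 − Φ(z × ratio)], with z the two-sided critical value at α.

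| r | (1 + r²)/2 | SE ratio | True error, nominal 0.05 | True error, nominal 0.0167 |
|---|---|---|---|---|
| 1.25 | 1.281 | 1.132 | 0.027 | 0.007 |
| 1.00 | 1.000 | 1.000 | 0.050 | 0.017 |
| 0.98 | 0.980 | 0.990 | 0.052 | 0.018 |
| 0.80 | 0.820 | 0.906 | 0.076 | 0.030 |
| 0.715 | 0.756 | 0.869 | 0.089 | 0.038 |
| 0.667 | 0.722 | 0.850 | 0.096 | 0.042 |

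**Step 2: what r could selection alone produce?** Assume a normally distributed screening measure of which the lowest fraction q is admitted. With c the q-quantile and λ = φ(c)/q, its variance after selection is v = 1 − cλ − λ². An activity measure that correlates ρ with the screening measure then has variance 1 − ρ²(1 − v).

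- Weak case: q = 0.5, ρ = 0.3 at baseline and 0.2 at 6 months. v = 0.363; variances 0.943 and 0.975; r = sqrt(0.943/0.975) = 0.98.
- Strong case: q = 0.2, ρ = 0.9 and 0.6. v = 0.219; variances 0.367 and 0.719; r = sqrt(0.367/0.719) = 0.715.

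Over q from 0.2 to 0.5 and the correlations tried between these extremes, r runs from about 0.71 to 0.98. The 6-month standard error is then 1% to 13% too small, and the per-pair error at nominal 5% is about 5.2% to 8.9%.

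**Step 3: simulation with REML fits.** N = 77, three arms, age and sex as covariates, correlation 0.5 between visits, 2,500 runs per setting:

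| r | Missing at 6 months | SE ratio | Error at 0.05 | Error at 0.0167 |
|---|---|---|---|---|
| 1.00 | 0% | 0.975 | 0.054 | 0.016 |
| 0.80 | 0% | 0.907 | 0.080 | 0.026 |
| 0.80 | 20% | 0.891 | 0.078 | 0.031 |
| 0.667 | 0% | 0.871 | 0.084 | 0.035 |
| 0.667 | 20% | 0.817 | 0.104 | 0.042 |
| 1.25 | 20% | 1.149 | 0.019 | 0.004 |

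A separate simulation (26/26/25 per arm, correlation 0.5, complete data, 800 runs) compared the planned model with one that lets the variance differ by visit. At r = 0.8 the familywise error of the three Bonferroni pairs was 7.2% against 4.2%. At r = 1 it was 4.6% against 5.0%, so the more flexible model costs almost nothing when it is not needed.

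**Step 4: the contrast of change.** The true variance of a participant's change is s0² + s1² − 2·cov. The model's is 2 × [(s0² + s1²)/2 − cov], which is the same. With complete data the simulated SE ratio for this contrast was 0.98 to 1.03; with 20% missing and r at or below 1 it was 0.92 to 0.99.

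**The case against.** The strongest objection is that nothing in the documents shows the variances differ. The entry rule concerns purposeful bouts reported by phone, whereas the outcome is free-living activity. Selecting on an imperfectly related item trims baseline spread only partly, and it also trims 6-month spread somewhat. All participants were encouraged toward the same national activity recommendations, which could even narrow the spread; the test would then be conservative. This stands. A reader might infer that baseline activity must be less spread and that the reported 6-month intervals are therefore too narrow. The documents do not support that: it is a conditional statement about data whose SDs are not given.

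A reader might also infer error rates above 10% per pair. In closed form that takes r near 0.6 (0.106), which is outside the range that selection alone produced under the assumptions above; it would need a further source such as uneven response. Dropout alone brings the simulated figure to about 10% at r = 0.667. The closed form also runs somewhat high at this sample size with complete data at that r: 9.6% against 8.4% simulated.

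Two further points limit the scope. The contrast of change, which the Statistical Methods section names as a purpose of the mixed models, is nearly unaffected with complete data. And the residual plot could reveal the problem: at r = 0.667 with complete data, simulated conditional residual SDs were 0.60 at baseline and 0.89 at 6 months. But the plan does not say that residuals would be viewed by visit, nor what would follow.

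Finally, the single variance is the natural reading of the model description, not an explicit statement. If a visit-specific structure was in fact fitted, saying so would close the point.

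**Conclusion.** The point holds in conditional form. As described, the model implies one variance for physical activity at both visits, and the planned 6-month comparisons depend on that. If spread is smaller at baseline, which the entry rule makes likely but not certain, the 6-month standard errors are too small by the factor sqrt((1 + r²)/2).

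For the assumed selection-only range, that is a modest effect: standard errors 1% to 13% too small and a nominal 5% per-pair error of about 5% to 9%. It grows with 6-month dropout or uneven response and reverses if spread shrinks. The baseline comparisons carry the opposite error. The size rests on assumed SD ratios, a normal selection model, and the plan's own 20% attrition allowance for the dropout case. Correcting the model does not depend on knowing the direction, because visit-specific variances give appropriate standard errors either way.

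**What to change.** For physical activity, replace the single-variance random-intercept structure with an unstructured 2×2 covariance over the two visits, or keep the random intercept and let the residual variance differ by visit. This can be done in both named packages (SPSS and R). Take the 6-month pairwise comparisons and their confidence intervals from that model, state the covariance structure in the Statistical Methods section, and report the SD of physical activity at each visit so that readers can see r.

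The cost is one extra variance parameter and, since the document already describes completed analyses, a short re-run. The 6-month intervals will be wider if the variance did rise; at r = 0.8, by 1/0.906 = 1.10, or about 10%. If the variances are equal, the loss is negligible.

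Using the same structure for cardiorespiratory fitness is optional. No entry criterion selects on fitness level, so the argument above does not carry over to it.

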In addition to behavioral counselling, SSBC participants also complete supervised progressive exercise during each of the six sessions. For this trial, SSBC participants provided additional consent for a sub-study for which they were randomly allocated to one of three conditions: HIIT was introduced and performed for all 6 sessions (HIIT-only); MICT was introduced and performed for all 6 sessions (MICT-only); and HIIT and MICT were introduced during sessions 1 and 2 in a randomized counterbalanced order, and participants were provided the choice of which exercise to perform during sessions 3-6 (CHOICE). In all three conditions, participants were able to choose whether to exercise on a treadmill, exercise bicycle, or elliptical. Exercise duration for each session was designed to elicit matching work volumes based on prescribed intensities for both HIIT and MICT during the progressive nature of the intervention. The use of progressive exercise was intended to help familiarize participants with exercise modalities they may not have been familiar with and/or ease the introduction of exercise to those who were previously insufficiently active. Exercise was individualized for each participant by prescribing exercise intensities based on their measured resting heart rate and HR_{max} from the stress test using the Karvonen formula. Exercise intensity compliance was measured during each exercise session via heart rate monitors and participants' RPE. Exercise intensity was recorded by the supervising community coach at the beginning and at 25%, 50%, and 100% of exercise completion, and coaches encouraged participants to adjust speed, resistance, or incline if target heart rate was not achieved. Following the 4-week supervised intervention, participants in all three conditions were encouraged to continue performing MVPA on their own according to Canada's physical activity recommendations for adults but were not told to exclusively perform

either HIIT or MICT due to the pragmatic nature of the SSBC program and this trial. Apart from condition allocation, all other aspects of the DPP were identical for all three conditions.

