Limited studies have been conducted that assess perceived autonomy support after adults are provided a choice between different types of exercise in an intervention. A study by Lonsdale and colleagues assessed the change in perceived autonomy support among adolescents enrolled in physical education programs. Comparisons between the control group (treatment as usual) and a group that was provided choice in what exercises were performed during class demonstrated a small-to-medium effect favoring the choice group (d = 0.39). Based on these results, we anticipated a crude small-to-medium effect size in favor of the choice condition in the present study ($d = \sim 0.40$). At an alpha level of .05 and 80% power, we estimated that 60 participants per condition (n = 180) were required to detect significant between-condition differences at this magnitude. Based on pilot findings by Locke and colleagues, this sample size was then increased by 20% to account for participant attrition, resulting in a total sample size of 216. The severe COVID-19 pandemic limitations impacted the ability to achieve the estimated sample size and data are thus reported for N = 77.

Randomization

SSBC participants were randomly allocated into one of the three arms of this study in a 1:1:1 allocation ratio by using a computer random-number generator that produced variable permuted block sizes. Conditions were stratified for biological sex (male and female) and age (18-45 and 46-75 years). Allocation sequencing was performed by a member of the research team not involved in any other aspect of this trial and allocation was concealed from participants until they began the intervention.

Blinding

Given the pragmatic nature of this trial and the fact that participants and community coaches needed to know which exercise modality to engage in during the exercise sessions, blinding of participants and those delivering the intervention was not possible. Data collected for each participant were blinded during data analysis by replacing the name of the allocated condition with a numerical digit known only to a member of the research team not involved in the data analysis phase so that data analysts would not be biased by condition allocation.

Statistical Methods

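### Does the analysis of perceived autonomy support need a pooled contrast of CHOICE against the two assigned-modality arms?

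*Combined protocol and SAP*

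**What the plan says.** The Outcomes section gives the aim for this outcome: "perceived autonomy support was measured post-intervention to discern any differences between conditions". Under Statistical Methods, a linear model is fitted to the single post-intervention score, adjusted for age and sex: "The model included treatment condition (i.e., HIIT, MICT, or CHOICE) as a fixed factor". The same section then names the source of the estimates: "Bonferroni-adjusted preplanned pairwise comparisons of estimated marginal means were conducted to derive effect estimates and accompanying 95% confidence intervals (CIs". It also sets the test level: "A two-sided alpha of .05 was used for all statistical analyses".

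The Sample Size section gives a direction, at d of about 0.40: "we anticipated a crude small-to-medium effect size in favor of the choice condition in the present study". It does not say whether the comparator is HIIT-only, MICT-only or both together. It describes the required numbers as those needed to detect between-condition differences.

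Under Small Steps for Big Changes, HIIT-only and MICT-only fix the modality for all six sessions. In the third arm, both modalities are introduced in sessions 1 and 2, and after that "participants were provided the choice of which exercise to perform during sessions 3-6 (CHOICE".

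**The concern.** The trial is built around offering a choice. Its expected effect favours the choice arm and is borrowed from a study of choice against usual teaching. Two of the three arms assign the modality. The natural single question is then whether choosing beats being assigned, and the natural estimate is CHOICE minus the mean of the other two arms. The fitted three-level factor yields this at no cost, yet the plan reports pairs only.

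The final sample is 77 against a target of 216, so intervals will carry most of the message. A reader would have to combine two wide, adjusted intervals to answer the choice question. The number of pairs under the Bonferroni adjustment is also not stated. If the pooled contrast were the real objective, the plan would be estimating something else, and less precisely.

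**Working it through.** **1. The plan's own figure.** The Sample Size section states: "At an alpha level of .05 and 80% power, we estimated that 60 participants per condition (n = 180) were required". With d = 0.40 and SD 1, the normal approximation gives, per arm:

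- one pair, two-sided: 2(1.960 + 0.842)²/0.40² = 98.1, so 99;
- pooled contrast, two-sided: 1.5(1.960 + 0.842)²/0.40² = 73.6, so 74;
- pooled contrast, one-sided: 1.5(1.645 + 0.842)²/0.40² = 57.96, so 58.

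Neither two-sided calculation gives 60. The one-sided contrast comes close but conflicts with the stated two-sided alpha. The sample size therefore does not show that a pooled contrast was the intended analysis. That 60 is not reproduced is a separate matter.

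**2. Objective against analysis.** Outcomes asks about any differences between conditions, Sample Size speaks of between-condition differences, and Statistical Methods compares pairs of conditions. These agree. The expected effect in favour of CHOICE fits CHOICE minus HIIT-only and CHOICE minus MICT-only as well as it fits a pooled contrast.

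**3. Precision at N = 77.** Assumptions: equal arms (n = 77/3 = 25.67), SD 1, no missing outcomes, df = 77 − 5 = 72 (three arms, two covariates).

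- Pair: SE = √(2/25.67) = .279.
- Contrast with weights 1, −½, −½: SE = √(1.5/25.67) = .242.
- Ratio: √(1.5/2) = .866, so 13% narrower like for like.

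| Estimate | 95% half-width (SD) | Power at means .4, 0, 0 |
|---|---|---|
| Contrast, unadjusted | .48 | 37% |
| Pair, unadjusted | .56 | 29% |
| Pair, Bonferroni for two | .64 | 20% |
| Pair, Bonferroni for three | .68 | 16% |
| Contrast as fourth Bonferroni member | .62 | 19% |

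From .68 to .48 is a fall of .20 SD. About .13 of it (.684 − .556) comes from dropping the adjustment and about .07 (.556 − .482) from pooling.

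**4. Detection with error control kept.** In simulation (arms 26/26/25, means .4, 0, 0), at least one CHOICE pair is significant in 26% of trials under the three-pair plan. The contrast as a fourth member reaches 19%. The chance of any rejection is 25% with four comparisons and 26% with three. If the unadjusted contrast is instead counted as a test beside the three pairs, familywise error under the global null is .071, against .044 for the pairs alone.

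**5. Where the contrast does worse.** If CHOICE equals one assigned arm and exceeds the other by .4, the contrast is .4 − (.4 + 0)/2 = .2 and its power is 13%. The pair that differs has 16% to 20%, and the omnibus test about 28% to 29%.

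**6. What it adds.** The point estimate is the mean of the two CHOICE pair differences. Its variance follows from the pair variances: ½[Var(CHOICE − HIIT) + Var(CHOICE − MICT)] − ¼Var(HIIT − MICT). With equal arms this is (2/n + 2/n)/2 − (2/n)/4 = 1.5/n, as in step 3. A reader given all three pairs can compute it.

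**7. What it would measure.** CHOICE participants are allocated their modality in sessions 1 and 2 and meet both modalities, while the other arms meet one. The contrast therefore mixes choice with exposure to both. Its equal weighting of HIIT and MICT also need not match the mix that CHOICE participants performed, which the documents do not give.

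**The case for a change.** The best case for adding the contrast is that it costs one statement from a model already fitted and could be shown beside the pairs as an estimate, not a test. It would give one interval on the question most readers will ask. Two adjusted CHOICE intervals alone do not supply it; the third pair or a covariance is needed. Even as a fourth Bonferroni member, its half-width (.62 SD) is below that of a pair adjusted for three comparisons (.68).

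All of this is true, and no pooled contrast appears anywhere in the documents. It makes the contrast a reasonable optional extra but does not show a fault in the plan. The documents describe an analysis already done, so the contrast would now be post hoc. It would sit outside the error control or cost the other pairs power: each CHOICE pair falls from 16% to 14% with four comparisons.

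The unlisted pairs are a missing detail. With three arms, and with analyst blinding achieved by "replacing the name of the allocated condition with a numerical digit known only to a member of the research team", all three pairs is the likely reading.

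**Conclusion.** The concern does not hold. The pairwise analysis is valid and matches the stated aim, and the documents state no pooled chosen-versus-assigned objective that it fails to meet. The contrast's real gain in precision is 13% of interval width. The rest of its apparent advantage over the planned pairs comes from giving up the multiplicity adjustment. With that adjustment kept, it detects less (19%) than the two CHOICE pairs together (26%). Experienced statisticians could reasonably differ over adding it.

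The widths and powers assume equal arms, SD 1, all 77 outcomes observed and, for the adjusted figures, the number of comparisons shown. The 13% needs only equal arms. The power comparison also assumes CHOICE 0.40 SD above two equal arms, the pattern most favourable to the contrast among those examined. The conclusion would change if the documents stated pooled choice against assignment as the objective, but they do not. The shortfall from 216 to 77 is the larger limit on what this outcome can show, and the contrast would not repair it.
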